#### **4.5.1.1 Ophthalmology Examination**

The following ophthalmologic variables will be summarized by descriptive statistics and will be presented at each visit where ophthalmologic assessment is performed, by eye, and overall:

- Visual acuity: method of assessment, visual acuity score (VAS) and result (normal, abnormal-not clinically significant, abnormal-clinically significant)
- Slit lamp biomicroscopy: location of biomicroscopy, biomicroscopy interpretation (normal, abnormal-not clinically significant, abnormal-clinically significant)
- Tonometry: intraocular pressure result
- Dilated fundus examination: interpretation (normal, abnormal-not clinically significant, abnormal-clinically significant)

#### **4.5.2 Additional Safety Assessments**

##### **4.5.2.1 Clinical Laboratory Evaluation**

The baseline value will be the last nonmissing value taken on or prior to first dose of study drug.

All laboratory results (hematology, biochemistry and urinalysis analysis) by local laboratories up to the end of treatment visit will be presented in standardized units. Both observed value and changes from baseline will be summarized using mean, standard deviation, minimum, maximum, and median for each scheduled visit. Plots of median, 25th percentile, and 75th percentile lab values at each scheduled assessment time will be provided for each laboratory parameter.

Frequency tabulations of qualitative clinical laboratory variables will be presented.

Laboratory results will be graded using NCI-CTCAE(Version 4.03), where possible. Parameters that have criteria available for both low and high values, i.e., hypo- and hyper-, will be summarized for both criteria. The same participant can be counted for both values if the participant has different laboratory values meeting each criterion. NCI-CTCAE grade of laboratory evaluations will be summarized by number and percentage of participants for each visit. Shift from baseline to maximum post-baseline NCI CTCAE grade will be summarized for each lab test. Laboratory abnormalities reported in  $\geq 10\%$  (All Grade) or  $\geq 5\%$  (Grade 3-4) of all subjects in SAF will be presented.

Laboratory results and NCI CTCAE grades for hematology and serum chemistry will be presented in data listings. Normal ranges will be documented and out-of-range values will be flagged. A separate listing of laboratory results with CTCAE grade 3 or higher will be presented.

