- This visit window is not applicable for Cycle 1 Day 1, could only be applied for the subsequent cycle.
- The EOT visit should be completed prior to the initiation of the next anticancer therapy.
- Brain scan and bone imaging will be performed at screening. Repeated at response assessment time points if metastases are identified at screening, or if metastasis is known or suspected, or as clinically indicated throughout the study.
- If HbA1c is elevated ($\geq 6.5\%$), refer participant to appropriate provider during Cycle 1 for glucose management. HbA1c needs to be tested in EOT evaluation as safety assessment.
- For women of childbearing potential only. A serum pregnancy test will be performed at baseline. A urine or serum pregnancy test will then be repeated on Day 1 of each cycle prior to study drug administration, at the EOT and post-treatment follow-up visit till 6 months after the last dose of study treatment administration.
- Not required for Cycle 1 if the assessments performed within 7 days, except for body weight, which should be measured on Day 1 of each cycle.
- Hematology tests should be collected at the following timepoints: Screening, Cycle 1 Day 1, Cycle 1 Day 8, Cycle 1 Day 15 and Day 1 of each subsequent cycle.
- Hematology and biochemistry tests may be collected or conducted locally up to 1 day prior to dosing. Local laboratory results must be reviewed prior to study drug administration in order to determine whether to proceed with dosing or whether dose modification is required.
- Clinical laboratory tests at screening and on Cycle 1 Day 8 are to be performed after the participant has been fasting in order to ensure accurate interpretation of lab values such as glucose values. Fasting status will be recorded in source documents. Fasting is not necessary for laboratory tests performed at all other visits. Lipid panel (total cholesterol, LDL, HDL, and triglyceride) is only required at Screening.
- Prior to performing 12-lead ECGs, participants should rest in supine position (or semi-recumbent, if supine is not tolerated) for 10 minutes. ECGs will be read and assessed locally.

Footnotes continued on next page

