7.2 Safety Assessments

7.2.1 Laboratory Assessments

- See [Section 10.6 Appendix 6: Laboratory Assessments] for the list of clinical laboratory tests (including hematology, biochemistry, urinalysis and HbA1c) to be performed and refer to [Table 1 Schedule of Assessments] for timing and frequency.
- The investigator must review the laboratory report, document this review, and record any clinically significant changes occurring during the study as an AE. The laboratory reports must be filed with the source documents.
- Clinical significance of out-of-range laboratory findings is to be determined and documented by the investigator or subinvestigator who is a qualified physician. Abnormal laboratory findings associated with the underlying disease are not considered clinically significant unless judged by the investigator to be more severe than expected for the participant's condition.

Laboratory tests will be sent to the local laboratory for analysis and entered into eCRF. Clinical laboratory tests will be performed locally prior to dosing. Tests will be obtained as indicated in the [Table 1 Schedule of Assessments]. If hematology and biochemistry tests were performed within 7 days prior to the first day of dosing, they do not need to be repeated on Cycle 1 Day 1. Clinical laboratory tests at screening, at screening and on Cycle 1 Day 8 are to be performed after the participant has been fasting in order to ensure accurate interpretation of lab test values such as glucose values. Participant can take food after fasting blood samples are obtained. Fasting status will be recorded in source documents. Fasting is not necessary for laboratory tests performed at all other visits. HbA1c will be obtained at screening/baseline and EOT visits. If HbA1c is elevated ($\geq 6.5\%$), refer participant to appropriate provider during cycle 1 for glucose management. Lipid panel, including total cholesterol, high-density lipoprotein cholesterol (HDL-C), low-density lipoprotein cholesterol (LDL-C) and triglyceride tests, will be only obtained at screening.

Additional assessments may be done to monitor AEs or as required by dose modification requirements. Additional laboratory tests should be performed according to institutional standard of care.

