  - Peripheral neuropathy, corneal disorders and blurred vision, dry eye, hyperglycemia, skin reactions, and infusion related reactions (IRR) are considered adverse events of special interest (AESI) for enfortumab vedotin. These are medical concepts of composite terms based on the search criteria (standard MedDRA query [SMQ] or sponsor specified query [SSQ]). Other AEs may be added to AESI as necessary. The search criteria for AESI will be maintained in a separate document and finalized prior to final database lock.
  - For selected AESI, time to onset of AESI will be calculated.

Time to onset of a specific AESI will be calculated as time from the first dose of study drug to the start of first treatment-emergent event that meets the respective search criteria.

Time to onset is defined at the participant level.
- Clinical laboratory variables

Below is a table of the laboratory tests that will be performed during the conduct of the study. Refer to the Schedule of Assessments in the protocol for study visit collection dates.

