## Laboratory Assessments

Panel/Assessments	Parameters to be Analyzed
Hematology	Hematocrit Hemoglobin Platelets Red blood cell count White blood cell count White blood cell count differential
Biochemistry	Albumin Alanine aminotransferase Alkaline phosphatase Aspartate aminotransferase Bicarbonate Blood urea Blood urea nitrogen Calcium Chloride Creatinine Hemoglobin A1c (HbA1c, screening and EOT only) High density lipoprotein (HDL) (Screening only) Glucose a Lactate dehydrogenase Low-density lipoprotein (LDL) (Screening only) Magnesium Phosphate Potassium Serum HCG for female participants Sodium Total and direct bilirubin Total cholesterol (Screening only) Total protein Triglyceride (Screening only)
Urinalysis	Specific gravity pH Blood Protein Glucose Bilirubin Microscopic (epithelial cells, bacteria, casts, crystals, WBC and RBC)
Serology	Hepatitis B and C at screening

EOT: end of treatment; HbA1c: hemoglobin A1c; HCG: human chorionic gonadotropin

a. Glucose at screening and on Cycle 1 Day 8 are required to be tested in fasting status in order to ensure accurate interpretation of glucose values. Fasting is not necessary for biochemistry laboratory tests performed at all other visits.

- Vital signs (systolic and diastolic blood pressures (mmHg), radial pulse rate (beats/minute) and body temperature (C) and weight
- 12-lead electrocardiogram (ECG)
- ECOG performance scores

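### Glucose change-from-baseline and low-grade shift summaries ignore fasting status, so they cannot separate a feeding effect from a drug effect

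*SAP*

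**What the plan says.** The fasting rule is in the footnotes to the Schedule of Assessments (Protocol 1.3): "Clinical laboratory tests at screening and on Cycle 1 Day 8 are to be performed after the participant has been fasting". The reason given there is correct interpretation of values such as glucose. The footnote then adds: "Fasting is not necessary for laboratory tests performed at all other visits". Protocol 7.2.1 and Appendix 6 repeat the rule, and so does the SAP's own laboratory table: "Glucose at screening and on Cycle 1 Day 8 are required to be tested in fasting status". On where the information is kept, Protocol 7.2.1 says: "Fasting status will be recorded in source documents".

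SAP 4.5.2.1 sets one rule for all laboratory parameters.
- Baseline: "The baseline value will be the last nonmissing value taken on or prior to first dose of study drug".
- By visit: "Both observed value and changes from baseline will be summarized using mean, standard deviation, minimum, maximum, and median for each scheduled visit".
- Worst grade: "Shift from baseline to maximum post-baseline NCI CTCAE grade will be summarized for each lab test".

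The same section plans median and quartile plots over visits, grade tables by visit, a table of abnormalities reaching 10% of participants (any grade) or 5% (Grade 3-4), and a listing of Grade 3 or higher results. SAP 4.11.2 and 4.11.3 keep all values in the non-PK analyses. Neither document flags, stratifies or restricts glucose by fasting status.

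**The concern.** The plan recognises that glucose needs a fasting sample to be interpreted properly, prints that rule in the SAP, and then analyses glucose as if the rule did not exist. A by-visit change from baseline is interpretable only if the two samples were taken under like conditions. Here one side of the comparison is usually fasting and the other is of mixed or unknown status.

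Hyperglycemia is one of the adverse events of special interest (SAP 4.5) and an important risk (Protocol 2.3.3). The study is also meant to show that safety in Chinese participants is consistent with that seen elsewhere (Protocol 2.1). In a randomised trial the same sampling habit would affect both arms and largely cancel. In a single-arm trial nothing removes it. What is at stake is the interpretability of the laboratory summaries for a named risk.

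**Working it through.** The documents give no figure on this point, so there is none to reproduce. The check compares the sampling rule with the analysis rule and then shows how far the answer depends on unknowns.

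**1. Which value becomes baseline.** Table 1 places screening biochemistry on Day -7 to -1. Protocol 7.2.1 waives the Cycle 1 Day 1 repeat if the tests were done within 7 days. Baseline is therefore usually the fasting screening sample. However, Protocol 6.5.2 asks for a glucose check before each dose. If a Day 1 pre-dose value is recorded, the SAP's last-value rule makes it the baseline, and it need not be fasting. One table can thus mix two kinds of baseline.

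**2. How many later values must be fasting.** The anticipated 8 months of treatment (Protocol 1.1) is 8 × 30.4375 / 28 = 8.7 cycles. Biochemistry is scheduled on Days 1, 8 and 15 of each cycle and at end of treatment. Leaving out Cycle 1 Day 1, which is not post-baseline, *c* full cycles give 3*c* − 1 + 1 = 3*c* post-baseline draws. Only Cycle 1 Day 8 must be fasting:

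| Full cycles | Post-baseline draws | Share required to be fasting |
|---|---|---|
| 2 | 6 | 1/6 = 17% |
| 4 | 12 | 1/12 = 8% |
| 8 | 24 | 1/24 = 4% |

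Held or omitted doses would change these counts somewhat.

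**3. Bias in mean change.** Let Δ be the mean fed-minus-fasting difference, *f* the proportion of samples at a visit that are fed, and *g* the proportion of baselines that are fed. Assume that Δ does not depend on who happens to be fed. With no drug effect, the expected mean change is (*f* − *g*)Δ. At Cycle 1 Day 8, where *f* = 0, it is −*g*Δ.
- All baselines fasting (*g* = 0): *f*Δ at other visits and 0 at Cycle 1 Day 8. For Δ = 20 to 40 mg/dL (assumed), this is 0 if everyone fasts, 10 to 20 if half are fed, and 20 to 40 if all are fed.
- Baselines as often fed as later samples (*g* = *f*): 0 at other visits and an apparent fall of *g*Δ at Cycle 1 Day 8.

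The sampling rule fixes none of *f*, *g* or Δ, so neither the size nor a uniform direction of the bias can be stated.

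**4. Worst value: an upper-end illustration.** The simulation has no drug effect. All of its inputs are assumptions: fasting mean 100 mg/dL, between-participant SD 15, within-participant SD 10, fasting baseline, 24 later draws, Cycle 1 Day 8 fasting, every other draw fed, and increment SD 75% of its mean.

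| Mean fed increment (mg/dL) | Mean change, Cycle 1 Day 8 | Mean change, other visits | Mean of (maximum − baseline) | Chance maximum exceeds 250 mg/dL |
|---|---|---|---|---|
| 0 | 0 | 0 | 20 | 0% |
| 10 | 0 | 10 | 34 | 0% |
| 20 | 0 | 20 | 55 | 0% |
| 30 | 0 | 30 | 77 | 0.03% |
| 40 | 0 | 40 | 101 | 1.8% |

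About 20 mg/dL of the maximum-minus-baseline figure comes from taking the largest of 24 noisy values and has nothing to do with feeding. The rest is the feeding effect: 55 − 20 = 35 at an increment of 20, and 101 − 20 = 81 at 40. Protocol 6.5.2 equates values above 250 mg/dL with Grade 3 or higher, so on these assumptions Grade 3-4 counts hardly move. The documents do not give the Grade 1 and 2 limits, so the number of low-grade shifts is not calculated. With 40 participants, the any-grade reporting threshold is 10% × 40 = 4 people.

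**The case against.** The strongest reply is that this is one analyte in descriptive, secondary safety tables, and that several stronger readings are not supported. Four parts of that reply stand.

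- *A reader might infer that glucose is unfasted at every other visit.* The text only makes fasting unnecessary there. Status is mixed or unknown, so the last rows of the simulation are an extreme and not an expectation.
- *A reader might infer that the plan will call the difference drug-induced hyperglycemia.* It does not. The laboratory tables attribute nothing. Hyperglycemia as an event of special interest comes from searches of adverse event terms, and relatedness comes from the investigator, with a missing assessment counted as related (SAP 4.5).
- *A reader might infer a rise at almost every visit.* If Day 1 values serve as baseline, the mismatch can move to Cycle 1 Day 8 and change sign.
- *A reader might infer that fasting status is missing from the eCRF.* The eCRF is not among the documents, and Protocol 10.1.7 says in general that participant data go into it. The documents show only that fasting status is recorded in source and that no planned analysis uses it.

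It is also fair to say that keeping all values is the cautious choice for a known risk. Limiting the worst-grade shift to fasting samples would lose later hyperglycemia. Further, the plan already has useful cover: HbA1c is in the biochemistry panel at screening and end of treatment, so its change is already summarised, and Grade 3 or higher values are already tabulated and listed.

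None of this supplies a like-for-like comparison for the glucose mean change or the low-grade shift. HbA1c and the Grade 3-4 listings complement those tables but do not make them interpretable.

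**Conclusion.** The concern holds in a limited form. Followed as written, the SAP compares a usually fasting baseline with glucose values of mixed or unknown fasting status, visit by visit and at the worst grade. With no control arm, those summaries cannot tell a feeding effect from a drug effect.

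The size is unknown from the documents. On the assumed 20 to 40 mg/dL difference, the bias in mean change runs from 0 to 20-40 mg/dL when baselines are fasting, and it can reverse at Cycle 1 Day 8 when they are not. Grade 3-4 counts are little affected under the assumptions shown. Event-based hyperglycemia rates and the confirmed response-rate test do not depend on these tables. The point is worth correcting because the measure concerns a named risk and the remedy is small; it does not threaten the study's main conclusion.

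**What to change.** 1. Carry the fasting status already recorded in source into the analysis data, with an eCRF field if it is not captured there now.
2. In SAP 4.5.2.1, define baseline glucose for this purpose as the last fasting value before first dose, and present change from baseline for fasting samples. Summarise samples not documented as fasting separately, as observed values.
3. Keep the all-sample worst-grade shift and the Grade 3 or higher listing so that no hyperglycemia is lost. Label them as mixed fasting status and add the shift split by fasting status.
4. State that the fasting glucose change is to be read alongside the HbA1c change from screening to end of treatment that is already planned.

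The cost is at most one data field filled from existing records, a short SAP addition and some extra table rows. No further blood draws and no change to treatment are needed. The drawback is that the fasting change from baseline will rest mainly on Cycle 1 Day 8, one week after the first dose, which is why item 4 matters.

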##### **4.5.2.2 Liver Safety Assessment**

The liver safety assessment will be summarized based on the measurements of alkaline phosphatase (ALP), alanine transaminase (ALT), total bilirubin, aspartate transaminase (AST), and their combination as defined below. The participant's highest value during the investigational period will be used. The number and percentage of participants meeting the criteria post-baseline will be summarized.

- ALT:  $> 3 \times \text{ULN}$ ,  $> 5 \times \text{ULN}$ ,  $> 10 \times \text{ULN}$ ,  $> 20 \times \text{ULN}$
- AST:  $> 3 \times \text{ULN}$ ,  $> 5 \times \text{ULN}$ ,  $> 10 \times \text{ULN}$ ,  $> 20 \times \text{ULN}$

- ALT or AST:  $> 3 \times \text{ULN}$ ,  $> 5 \times \text{ULN}$ ,  $> 10 \times \text{ULN}$ ,  $> 20 \times \text{ULN}$
- ALP:  $> 1.5 \times \text{ULN}$
- Total bilirubin:  $> 2 \times \text{ULN}$
- (ALT or AST  $> 3 \times \text{ULN}$ ) and Total bilirubin  $> 2 \times \text{ULN}^*$
- (ALT or AST  $> 3 \times \text{ULN}$ ) and Total bilirubin  $> 2 \times \text{ULN}$  and ALP  $< 2 \times \text{ULN}^*$

\*Combination of values measured on the same day or within 1 day apart.

The denominator for each criterion will be the number of participants who have at least one value postbaseline.

In addition, participants with the post-baseline liver function test results that are consistent with the Hy's law criteria will be listed.

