10.4 Appendix 4: Liver Safety Monitoring and Assessment

The purpose of this appendix is to provide guidance for the monitoring of DILI during the course of the study. It should be noted that this section does not specify the end-of-study analyses of liver enzymes. The end-of-study liver enzymes analyses will be described in the SAP. Any participant enrolled in a study with active drug therapy and who reveals an increase of serum aminotransferases (AT) to $> 3 \times$ ULN (to $> 5 \times$ ULN in participants with liver metastases) or TBL $> 2 \times$ ULN should undergo detailed testing for liver enzymes (including at least ALP, ALT, AST and TBL). Testing should be repeated within 72 hours of

notification of the test results. Participants should be asked if they have any symptoms suggestive of hepatobiliary dysfunction.

Definition of Liver Abnormalities

Confirmed abnormalities will be characterized as moderate and severe where ULN is as shown below.

Table 11 Moderate and Severe Liver Abnormalities

	ALT or AST		TBL
Moderate	$> 3 \times \text{ULN}$ (in participants without liver metastases), $> 5 \times \text{ULN}$ (in participants with liver metastases)	or	$> 2 \times \text{ULN}$
Severe	$> 3 \times \text{ULN}$	and†	$> 2 \times \text{ULN}$

ALT: alanine aminotransferase; AST: aspartate aminotransferase; TBL: total bilirubin; ULN: upper limit of normal

†Samples taken simultaneously or within maximum 24 hours.

In addition, the participant should be considered to have severe hepatic abnormalities for any of the following:

- ALT or AST $> 8 \times \text{ULN}$
- ALT or AST $> 5 \times \text{ULN}$ for more than 2 weeks (in the absence of liver metastases)
- ALT or AST $> 3 \times \text{ULN}$ and† TBL $> 2 \times \text{ULN}$ or international normalized ratio (INR) > 1.5 (If INR testing is applicable/evaluated)
- ALT or AST $> 5 \times \text{ULN}$ and† (TBL $> 2 \times \text{ULN}$ in participants with liver metastases)
- ALT or AST $> 3 \times \text{ULN}$ with the appearance of fatigue, nausea, vomiting, right upper quadrant pain or tenderness, fever, rash and/or eosinophilia ($> 5\%$)

† Samples taken simultaneously or within a maximum of 24 hours.

The investigator may determine that abnormal liver function results, other than those described above, may qualify as moderate or severe abnormalities and require additional monitoring and follow-up.

Follow-up Procedures

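### SAP 4.5.2.2 applies a whole-period highest-value rule to the combined liver criteria as well as the single tests, which conflicts with the 1-day footnote and leaves the combined counts open to error in either direction

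*SAP*

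**What the plan says.** SAP 4.5.2.2 (Liver Safety Assessment) sets the scope as four analytes, ending with "aspartate transaminase (AST), and their combination as defined below". The next sentence gives the rule for choosing values: "The participant's highest value during the investigational period will be used". No row is exempted. The count is then defined: "The number and percentage of participants meeting the criteria post-baseline will be summarized".

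Seven rows follow. Five are single-test rows: ALT, AST, ALT or AST, ALP, and total bilirubin. Two are combined rows marked with an asterisk:

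- ALT or AST >3×ULN with total bilirubin >2×ULN;
- the same, with ALP <2×ULN in addition.

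The asterisk leads to: "Combination of values measured on the same day or within 1 day apart". The denominator is also given: "The denominator for each criterion will be the number of participants who have at least one value postbaseline". Separately, "participants with the post-baseline liver function test results that are consistent with the Hy's law criteria will be listed".

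Protocol 10.4 (Appendix 4) uses a similar timing idea for monitoring during the study ("Samples taken simultaneously or within maximum 24 hours"). It does not define the final table: "The end-of-study liver enzymes analyses will be described in the SAP". The SAP therefore governs this analysis.

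**The concern.** Taking a participant's highest value and requiring values from the same day or the next are two different derivations. For a single-test row the first is exactly right. For a combined row it is not, because the highest ALT, the highest bilirubin and the highest ALP need not come from the same sample.

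The ALP component raises a further difficulty. It is an upper bound, so testing the highest ALP of the whole period asks whether ALP was always below 2×ULN. The criterion needs to know whether it was below 2×ULN when ALT or AST and bilirubin were raised.

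Two programmers could follow this section in good faith and produce different counts for the rows that matter most to a reader looking for drug-induced liver injury. Different peak dates are plausible in this trial. Biochemistry is scheduled on Days 1, 8 and 15 of each cycle (Protocol Table 1). Protocol 10.4 adds a repeat within 72 hours after an elevation, and testing 2 to 3 times weekly once a moderate abnormality is confirmed. The participants of interest will have many samples.

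**Working it through.** The liver section states no rate or expected count, so there is no plan figure to reproduce. The check is of logic.

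**Step 1: when the highest value is sufficient.** For a single test with threshold c, max(x) > c is true exactly when some post-baseline x exceeds c. The five single-test rows are therefore correct as written, including the ALT-or-AST row.

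**Step 2: when it is not.** The first starred row needs some ALT (or AST) >3 and some bilirubin >2 dated within 1 day of each other. Knowing max(ALT) >3 and max(bilirubin) >2 does not establish this. Requiring the two maxima themselves to lie within 1 day is stricter than the criterion. For the second starred row, max(ALP) <2 means that every ALP was below 2, which is stricter than ALP <2 in the relevant window.

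**Step 3: three readings of the section.**

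1. Peak values only, and the peaks must lie within 1 day of each other.
2. Peak values only, with the window ignored.
3. Any set of post-baseline values within 1 day that meets all components.

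**Step 4: four invented records.** Values are multiples of ULN, given as ALT / bilirubin / ALP. AST is assumed not to contribute. Every record starts at 1 / 0.8 / 1 on day 1.

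- A: day 8, 6 / 1.8 / 1.2; day 15, 4 / 2.5 / 1.4; day 22, 1.5 / 1.2 / 1.3.
- B: day 8, 6 / 2.5 / 1.2; day 15, 2 / 1.5 / 1.1.
- C: day 8, 6 / 2.5 / 1.2; day 29, 2 / 1.5 / 2.4.
- D: day 8, 6 / 1.0 / 1.2; day 57, 1 / 2.5 / 1.3.

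Counted in first starred row / second starred row:

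| Record | Reading 1 | Reading 2 | Reading 3 |
|---|---|---|---|
| A: peaks 15 − 8 = 7 days apart, both over threshold on day 15 | no / no | yes / yes | yes / yes |
| B: peaks on the same day | yes / yes | yes / yes | yes / yes |
| C: concurrent on day 8, ALP peak of 2.4 later | yes / no | yes / no | yes / yes |
| D: elevations 57 − 8 = 49 days apart, never together | no / no | yes / yes | no / no |

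Record A is a true concurrent case (4 >3 and 2.5 >2 in the day 15 sample) that reading 1 drops. Record D is not a concurrent case, yet reading 2 counts it. Record C belongs in the second starred row, because ALP was 1.2 on day 8. Both peak-based readings drop it, because max(ALP) = 2.4 is not below 2. Only reading 3 classifies all four records as the criteria intend.

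**Step 5: size.** With 40 participants in the denominator, one participant is 1/40 = 2.5%. A single misclassification moves a row from 0% to 2.5% or the reverse. If fewer than 40 have a post-baseline value, the step is slightly larger.

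**The case against.** The best answer is that a specific footnote governs its own rows. On that view the highest-value sentence serves the unstarred rows and the footnote replaces it for the starred ones, which is reading 3. The footnote has little purpose if it only compares the dates of two whole-period peaks, and Protocol 10.4 applies a concurrent-sample rule to the same pair of tests. This may well be what was intended, and it stands as a reasonable reading. It does not remove the point, because the scope sentence expressly includes the combinations and the rule that follows makes no exception. The SAP never says that the footnote replaces the rule.

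The second answer is that cases would surface elsewhere. Protocol 10.3.1.2 treats potential Hy's law cases as important medical events to be reported under the serious adverse event procedure. Protocol 10.4 requires repeat testing and a liver abnormality form, and asks that the sponsor be told of severe abnormalities possibly attributable to the product. SAP 4.5.2.1 lists laboratory results with out-of-range values flagged. The Hy's law listing refers to post-baseline results and is not expressly tied to peaks. This largely stands and is why the point is minor. A listing gives no count or percentage, however, and no derivation is given for it, so table and listing could disagree within one report.

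A reader might infer more: that concurrent cases with different peak dates are definitely not counted, that the rule can only lose cases, or that one lost case would change the liver-safety conclusion. The documents do not support these. The first holds only if the peak rule and the window are applied together. The second fails on record D. The third overlooks the other routes by which a case would be seen.

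**Conclusion.** The concern holds as a conflict of wording that can produce a wrong count in the two starred rows. If the highest-value rule and the footnote are both applied literally, some concurrent elevations may be missed. If the window is ignored, non-concurrent peaks may be counted falsely. The ALP component is the clearest fault, since using the peak for an upper-bound criterion removes a true case under either peak-based reading.

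The size is small: one participant, or 2.5% of 40, per misclassification, in a descriptive safety table. How often it would happen cannot be estimated from the documents, which give no ALT or bilirubin time courses. The four records show what is possible, not how likely it is. They also leave AST aside. Because the criterion accepts either transaminase, an AST peak above threshold within 1 day of the bilirubin peak would keep a participant such as record A in the first starred row. The primary analysis and the sample size are unaffected. Severity: minor.

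**What to change.** In SAP 4.5.2.2, limit the highest-value sentence to the single-test rows, including the ALT-or-AST row. For the two starred rows, state that all post-baseline results are evaluated, and that a participant is counted if any set of values within 1 day has ALT or AST >3×ULN and total bilirubin >2×ULN. For the second starred row, require ALP <2×ULN from that same window. It would be sensible to say that the Hy's law listing uses the same derivation, so that table and listing agree.

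The cost is about one sentence of SAP text and the matching programming specification. ALT, AST, ALP and bilirubin are all in the one biochemistry panel (Protocol Table 12 and the laboratory table in SAP 4.5), so no new data are needed.
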